# Flow diagram for randomized, controlled trial

## 6.0 Enrollment/Randomization

40 school age children and youth with ASD will be recruited through local community agencies (e.g., schools, churches, and rehabilitation centers), social media platforms (e.g., Facebook and Reddit) and direct contact. Participants will be divided into 2 groups based on their age such as, group 1: 7-14 years and group 2: 15-22 years. Co-PI will allocate participant based on the coin flip such that heads = intervention group and tails = control group. The next participant in the same age range (range 1: 7-14 years, range 2: 15-22 years) will be assigned to the other group.

The process will continue till there are 10 participants in each age range for each intervention and control group (total n = 40).

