# 7.0 Study Procedures

1. Prior to day 1: Informed consent materials, a screening questionnaire, and Autism Spectrum Screening Questionnaire (ASSQ) will be sent electronically to parents/caregivers. Participants and parents/caregivers in both groups will be given access to a video of the data collection space, intervention space setting, and a short introduction of the research personnel for review. If the participants are 18 years or older, this information will be shared with the participants directly and they will fill the questionnaires. If the participant is less than 18 years old, the information will be shared with the parent/legal guardian to be completed. Additionally, The ASSQ is a commonly used valid and reliable 27-item checklist to be filled in by parent/caregiver for assessing symptom characteristics of ASD. The ASSQ can be completed in 10 minutes using a 3-point Likert scale with possible score range being 0 of 54 with 19 being a cut off for a parent/caregiver rating identifying ASD. This tool will be used as a part of demographic screening of the participants prior to the pre-intervention day and used to better describe individual autism symptoms than is available in a medical or educational diagnosis. The researcher will subsequently contact participants and parent/caregiver to review the information, check for understanding, (particularly the terminology used in the ASSQ), assess eligibility via screening tool and address any other questions prior to study inclusion and visit.

Study participation will require 9 visits: 1 pre-intervention visit, 6 intervention visits, 1 post-intervention visits and 1 retention visit. Participants will receive \$10 Amazon or Kroger gift card after completing each session with total possible compensation of \$90.

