## 4. Post-intervention/session 8 and 9:

Static and dynamic balance will be reassessed as previously described to examine retention effects of the VR active gaming intervention (see study calendar). Session 8 will be at least 3-5 days after session 7. Parent/caregiver will return the Nintendo Switch Sports to the researcher. Session 9 will be 4 weeks after session 7. Each session will be for approximately 60 minutes.

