# 11.0 Statistical Considerations

According to prior research study examining the similar paradigm using Xbox games (Ghobadi et al. 2019), we predict the medium effect size (f=0.25) to detect significant changes within groups, between groups and effect of timepoint on static and dynamic balance. Power analysis

(using G\*power 3.1.9.7 software) indicates 14 subjects in each group to have 0.8 power to detect this effect (alpha 0.05). To account for the likelihood of attrition and noncompliance, total 40 participants are being recruited. Data from participants who engage in all the intervention sessions will be included in the analysis.

SPSS (Statistical Package for the Social Sciences) and MATLAB will be used for processing and analyzing the data. Participants demographic and health characteristics will be compared using paired sample t-tests. Intention to treat analysis will be used for addressing effects of treatment or control on static and dynamic balance. The dependent variables for static balance include: 1) sway area of 95% confidence ellipse for center of pressure(mm²), 2) direction of center of pressure sway as anteroposterior and mediolateral (mm). The dependent variables for dynamic balance are: 1) step length (m), 2) stride length (m), 3) step width (m), 4) double support period (sec), 5) cadence (steps/min) and 6) gait velocity (meters/min). Total PBS score will be dependent variable for both static and dynamic balance.

Two-way repeated measures ANOVA (analysis of variance) will be used to determine 1) within intervention and control group, for assessing the main effect of group, 2) between intervention and control group for assessing main effect of time, and 3) between - within interaction for assessing the interaction term. Statistical significance will be declared if  $p \le 0.05$  (two-tailed).

[name] ([contact]) will assist with the statistical considerations.

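### Section 11.0 names two incompatible analysis sets for the same balance outcomes, session completers and intention to treat, and does not say which is primary

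*Combined protocol and SAP*

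**What the plan says.** Three sentences in Section 11.0 bear on who is analysed. The sample-size paragraph raises the total above the calculated 14 per group: "To account for the likelihood of attrition and noncompliance, total 40 participants are being recruited". The next sentence is "Data from participants who engage in all the intervention sessions will be included in the analysis". The following paragraph, on analysis, says "Intention to treat analysis will be used for addressing effects of treatment or control on static and dynamic balance".

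The outcomes are the same under both rules. Section 11.0 lists the sway and gait variables and adds "Total PBS score will be dependent variable for both static and dynamic balance". The model is given as "Two-way repeated measures ANOVA (analysis of variance) will be used to determine" the group, time and interaction effects.

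Section 7.0 sets the visits as "1 pre-intervention visit, 6 intervention visits, 1 post-intervention visits and 1 retention visit", so completing the intervention means six sessions, and outcomes are measured three times (Sessions 1, 8 and 9).

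No section ranks the two sets, defines an intention-to-treat or per-protocol population, or gives a rule for missing assessments. Section 3.1 (item 2) allows a gait assessment that cannot be done to be rebooked twice, after which the participant is dismissed. Section 10.0 covers withdrawal by the participant and stopping by the researchers. Neither says what happens to those participants' data in the analysis.

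**The concern.** A reader cannot tell from Section 11.0 who enters the main efficacy analysis. Three things follow.

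- **Selection.** Attending every session happens after allocation. Restricting to those who did so can undo the comparability that allocation is meant to give. The comparison is at risk if completion differs between arms or relates to outcome differently by arm. The arms do different things at home (chosen video games or set balance exercises), so equal completion cannot be taken for granted.
- **Choice after seeing data.** Two unranked sets leave the choice open. An unranked plan does not in itself raise the false-positive rate. Picking the set because of its result does.
- **Deliverability.** Repeated-measures ANOVA in its usual form needs every time point. With no missing-data method, an analysis labelled intention to treat would become complete-case wherever Session 8 or 9 is missing.

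**Working it through.** **1. The two rules side by side.** Take a participant who attends five of the six sessions and both later assessments. Under the completer sentence this person is out; under intention to treat, in. The rules agree only if everyone attends everything or if the first sentence is not a rule about analysis (see the objection).

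**2. The plan's own sample size.** Inputs from Section 11.0: f = 0.25, alpha 0.05, power 0.80. From Section 7.0: m = 3 assessments. Assumed, because not stated: correlation rho = 0.5 and sphericity. For the group-by-time interaction with two groups, lambda = f² × N × m / (1 − rho), with df 2 and 2(N − 2).

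- N = 28: lambda = 0.0625 × 28 × 3 / 0.5 = 10.5, power 0.812. The stated 14 per group is reproduced.
- N = 40: lambda = 15.0, power 0.935.

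**3. How far the sets could differ.** No attendance rate is given. If attendance were independent between sessions at 0.90, 0.95 or 0.98 (assumed), the share attending all six would be 0.90⁶ = 0.531, 0.95⁶ = 0.735 or 0.98⁶ = 0.886. That is about 21, 29 or 35 of 40.

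**4. Choosing the set by its result.** Simulation: 100,000 trials per row, no true effect, 20 per arm, three time points, rho = 0.5. Non-completion is random and equal between arms, and every visit is observed. Each analysis alone has a type I error of 4.9-5.1%.

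| Non-completers per arm | Share | Either set significant |
|---|---|---|
| 1 | 5% | 6.1% |
| 2 | 10% | 6.6% |
| 4 | 20% | 7.2% |
| 6 | 30% | 7.8% |

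With rho = 0.3 or 0.7 the range is 6.5-7.7% at 10-30%. If non-completers also miss Session 8 or 9 and are dropped by the ANOVA, the two sets converge and the excess shrinks towards zero.

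**5. Selection bias in the completer set.** Same design, no true effect. The lowest-ranked participants are removed on a score that correlates r with change at Session 8 (SD 1). All rates are assumed.

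| Loss by arm | Bias in SD (r = 0.3 / 0.5 / 0.8) | Type I error |
|---|---|---|
| 20% v 20% | 0 / 0 / 0 | 5.1 / 5.5 / 6.4% |
| 15% v 5% | 0.048 / 0.080 / 0.129 | 5.2 / 5.8 / 7.1% |
| 20% v 10% | 0.045 / 0.076 / 0.121 | 5.3 / 5.8 / 7.2% |
| 30% v 10% | 0.088 / 0.147 / 0.235 | 5.6 / 6.7 / 10.0% |

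The first row is the comparator. At modest loss, much of the small excess in type I error is present even with equal loss and zero bias, so it should not be credited to differential completion. The last row is an extreme case.

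**6. Power cost of intention to treat.** Suppose a share q does not complete and gains nothing, so f becomes 0.25 × (1 − q) at N = 40. Completers keep f = 0.25 with N = 40 × (1 − q).

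| q | lambda, all 40 | Power, all 40 | Power, completers (N) |
|---|---|---|---|
| 10% | 12.15 | 0.874 | 0.906 (36) |
| 20% | 9.60 | 0.782 | 0.866 (32) |
| 30% | 7.35 | 0.660 | 0.812 (28) |

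Simulation, which adds the spread from mixed responses, gives 0.86, 0.76 and 0.62 for all 40, and 0.81 at q = 15%. These figures assume full follow-up of non-completers, so they are a best case. They also depend on rho: at 0.3 the formula gives 0.74, 0.63 and 0.51; at 0.7 it gives 0.98, 0.95 and 0.88. If non-completers keep half the effect, the rho = 0.5 values are 0.91, 0.87 and 0.83.

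**The case against.** The strongest reply is that there is no contradiction. The first sentence does not contain the word only, and it closes the sample-size paragraph. It might describe who counts towards the 14 per group, leaving the intention-to-treat sentence, which names the effects it covers, to govern efficacy. Part of this stands: the exclusion is inferred, not spelled out. But the sentence speaks of inclusion in the analysis and comes straight after the increase for dropout and non-adherence. The natural reading is a completer rule. A plan should not leave the main analysis set to inference.

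A second reply is that non-completion may be low, since Section 7.0 lets sessions be fitted to the family's schedule. That is possible, and it limits the likely size of the problem, though Section 11.0 itself plans for non-adherence.

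Two stronger readings are tempting and are not supported.

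- A reader might infer that the follow-up timing contradicts itself, because Section 7.0 item 4 says "Session 8 will be at least 3-5 days after session 7" while Section 14.0 counts from the final intervention day. As planned, these are the same day. The text is merely silent about someone who never reaches session 7. Section 10.0 is likewise silent on analysis, which is not a conflict with intention to treat.
- A reader might infer an expected loss of 30% from 28/40. The total of 40 is also four cells of ten under Section 6.0, and no rate is stated.

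**Conclusion.** The point stands and should be corrected before analysis. Section 11.0 gives two incompatible analysis sets for the same outcomes and ranks neither. This rests on the text and needs no calculation.

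The actual size is unknown because the documents contain no completion rates. The 6-8% type I error applies only if the set is chosen by its result, and under the assumptions in step 4. It is not a forecast for this trial. Bias under the completer rule ranges from zero to 0.235 SD over the assumed scenarios, and below 0.1 SD for a 10-point difference in loss with r up to 0.5.

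The missing-data gap is part of the same problem. Dismissal after failed gait assessments, withdrawal and researcher stops can each leave a time point missing, and the planned ANOVA would then return a complete-case set under an intention-to-treat label.

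**What to change.** 1. Delete the sentence on participants who complete every session, or relabel that set as a per-protocol sensitivity analysis.
2. State that the primary analysis includes all allocated participants in the arm assigned, regardless of sessions attended.
3. Replace the complete-case repeated-measures ANOVA with a linear mixed model (group, time, group-by-time) that uses all available assessments, and state its missing-at-random assumption.

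As a clarification only, say how Sessions 8 and 9 are dated for someone who does not reach session 7. No change is proposed to who is stopped, dismissed or continued.

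The cost is mostly wording. The real downside is dilution, as in step 6. With no effect in non-completers and rho = 0.5, N = 40 holds 0.80 power up to about 15% non-completion. By formula, 0.80 needs a total of 34, 42 or 54 at 10%, 20% or 30%. If the team expects more than about 15%, it should restate power for the full set. The completer result remains reportable as a sensitivity analysis.

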# 5.0 Study Design

Single blinded randomized controlled clinical trial design will be used. After obtaining the consent material, potential participants will be screened using inclusion and exclusion criteria, ASSQ and screening questionnaire. Co-PI will create and administer the assignments. Participants will be blinded to the allocation process to either the intervention or the control group.

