# 2. Pre-intervention/session 1:

2.1 As part of familiarization, participants will be shown and allowed to handle the different data collection instruments and ask questions. The intervention group will be shown the Nintendo Switch to get familiarized with their operation and functions. Parents/caregivers of the participants (under 18 years of age) in the intervention group will be handed over the Nintendo Switch Sports

to be connected at their home for the duration of intervention. Participants 18 years of age or older will be given the device. Researchers will provide any technological assistance required for this purpose.

2.2 Weight will be recorded using a calibrated scale and height measured using a stadiometer. The Edinburgh Handedness Inventory-short form (EHI-SF) will be used to assess hand-preference. It is a valid and reliable 4-item checklist of everyday tasks and participants score their hand preference on 5-point Likert scale (for each item, always right= 100, usually right= 50, usually left= 50, always left= -100). A researcher will read the rating scale to those with low literacy level. Handedness will be determined using a laterality quotient. The laterality quotient is interpreted as left handers (-100 to -61), mixed handers (-60 to +60) and right handers (61 to 100). Hand length will be calculated using a tape cloth, measured from greater tuberosity to distal end of middle digit on the right hand and leg length iliac crest to ground on the right leg.

Participants will be shown the different data collection instruments to handle, get familiarized and ask questions. Participant's hand dominance will be recorded using the Edinberg Handedness Inventory-short form. Participant's foot dominance will be recorded by asking them to kick an imaginary ball placed on the ground in front of them. Practice trials for balance and gait assessments will be conducted to ensure understanding of the protocol. Baseline assessments for posture and gait will be performed.

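### Paired t-tests are planned for demographic and health characteristics without any defined pairs, so the baseline p-values would depend on row order (minor; outcome analyses unaffected)

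*Combined protocol and SAP*

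**What the plan says.** The sentence at issue is in section 11.0 (Statistical Considerations): "Participants demographic and health characteristics will be compared using paired sample t-tests". It names no pairing variable, no time point and no arms.

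Four other places bear on how to read it.

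- Section 5.0 (Study Design): "Single blinded randomized controlled clinical trial design will be used". There are two parallel arms and nobody is in both.
- Section 6.0 (Enrollment/Randomization): a coin is flipped, with "heads = intervention group and tails = control group", and then "The next participant in the same age range (range 1: 7-14 years, range 2: 15-22 years) will be assigned to the other group". Allocation continues until each age range has 10 people per arm, so 20 against 20.
- Section 7.0, session 1: "Weight will be recorded using a calibrated scale and height measured using a stadiometer". Handedness and limb lengths are also taken at this visit. The calendar in section 8.0 leaves these demographic measures out of sessions 8 and 9.
- Section 11.0, outcome analysis: the two-way repeated measures ANOVA treats intervention against control as a comparison between different people.

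**The concern.** A paired t-test analyses differences within defined pairs. Here the two candidate sources of pairs are the same person at two times, or a participant in one arm matched to a participant in the other. The first is ruled out for the demographic measures because they are recorded once. The second is not specified anywhere. An analyst following the sentence literally would place the two arms in adjacent columns and let the spreadsheet order decide who is paired with whom.

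Two analysts with identical data could then report different p-values for the same characteristic, one suggesting balance and the other imbalance. A t-test of either kind also does not suit the categorical items collected, such as foot dominance or the yes/no screening questions on previous therapy and video-game use, should these be among the characteristics compared.

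**Working it through.** **Which comparison is meant.** Section 7.0 places the demographic measures at session 1, and section 8.0 excludes them from the later assessments. No before/after pairs exist, which leaves a comparison between arms. This is an inference, since section 11.0 does not say so, but it is the only workable reading.

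**The plan's own figure.** Section 11.0 gives 14 per group for power 0.8 at f = 0.25 and alpha 0.05. Take the group-by-time interaction with k = 2 arms, m = 3 assessments (sessions 1, 8 and 9) and N = 28. Assume a correlation of 0.5 between assessments and sphericity, since the documents state neither.

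- Noncentrality: f² × N × m / (1 − 0.5) = 0.0625 × 28 × 3 / 0.5 = 10.5
- Degrees of freedom: (2 − 1)(3 − 1) = 2 and (28 − 2)(3 − 1) = 52
- Power: 0.812

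The 14 per group reproduces. The baseline test does not enter this calculation, so changing that test leaves the sample size alone.

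**Why row order matters.** Take n per arm, SD 1 in each arm and an observed difference d. Let r be the correlation between the two columns as they happen to be lined up.

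- Independent test: t = d / √(2/n), with 2n − 2 degrees of freedom.
- Paired test: t = d√n / √(2 − 2r), which equals the independent t divided by √(1 − r), with n − 1 degrees of freedom.

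Re-sorting one column changes r and nothing else. With n = 20 and an assumed d of 0.6:

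- Independent: t = 0.6 / √0.1 = 1.897 on 38 df (critical value 2.024), p = 0.065, whatever the order.
- Paired with r = 0: t = 1.897 on 19 df (critical value 2.093), p = 0.073.
- The paired test reaches p ≤ 0.05 once 1 − r ≤ (1.897/2.093)² = 0.82, that is, once the accidental correlation is about 0.18 or more.

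A correlation of that size is common by chance in 20 unrelated rows. Permuting one column 20,000 times on constructed data gave:

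| Observed difference, n per arm | Independent p | Paired p, central 95% of orderings | Orderings at p ≤ 0.05 |
|---|---|---|---|
| 0.6 SD, 20 | 0.065 | 0.020 to 0.130 | 23% |
| 0.5 SD, 20 | 0.122 | 0.047 to 0.203 | 3% |
| 0.3 SD, 20 | 0.349 | 0.217 to 0.440 | 0% |
| 0.6 SD, 14 | 0.125 | 0.036 to 0.222 | 5% |

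In the first row the full range was about 0.002 to 0.17. The lower end varies between about 0.001 and 0.003 with the constructed dataset. The effect is largest for differences near the significance threshold and small for modest ones.

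**Error rate and power with rows in random order.** A simulation of 40,000 datasets with 20 per arm and no true difference gave a type I error of 0.050 for the paired test and 0.051 for the independent test. Power to detect an assumed imbalance of 0.8 SD is 0.67 paired against 0.69 independent at 20 per arm, and 0.50 against 0.53 at 14 per arm.

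**The case against.** The strongest reply is that a pairing was available by design. Section 6.0 sends the next participant in the same age range to the opposite arm, so consecutive enrollees could be treated as pairs, and with that rule fixed in advance the p-value would not depend on row order. This stands as far as it goes: it would be wrong to infer that no basis for pairing exists. But section 11.0 does not link the test to these enrollees, the age ranges are eight years wide (7–14 and 15–22), and the outcome ANOVA makes no use of such pairs. Dropout would also break them if the comparison were restricted to completers.

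Three further inferences are tempting and not supported.

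- *That the test has an inflated false-positive rate.* With rows in random order it stays at 5%. A rate of about 0.61 appears only if both columns are sorted on the variable being tested, and nothing in the documents suggests that.
- *That the test cannot be run with unequal arms.* It can, by dropping incomplete pairs. Moreover, these measures are taken before the intervention, and a table of everyone allocated would be 20 against 20.
- *That the whole baseline table fails.* Means, SDs and counts do not depend on the test. Readers can judge comparability from those, so the partly predictable allocation in section 6.0 is a separate matter and does not add weight here.

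The sentence may also simply be a slip for independent samples. That would explain it, but the text would still need correcting.

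**Conclusion.** The point holds at minor severity. As written, the plan names a paired test for what can only be inferred to be a comparison of two arms of different people, and it defines no pairs. The consequence is arbitrary, irreproducible baseline p-values. In the worked case one dataset gives p anywhere from about 0.002 to 0.17, against a single value of 0.065 from the independent test. That size rests on an assumed observed difference of 0.6 SD with 20 per arm; the documents give no expected imbalance, and the table above shows how the effect shrinks at 0.3 and 0.5 SD.

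A reader might go on to infer that the trial's balance results or its conclusions are invalid. The documents do not support that: the descriptive summaries, the 14 per group, the 40 recruited and the outcome ANOVA do not depend on this sentence.

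**What to change.** Replace the sentence in section 11.0 with:

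> Baseline characteristics will be summarised by arm (mean and SD, or n and %) with standardised differences.

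If tests are kept, specify independent-samples t-tests for continuous characteristics and Fisher's exact or chi-square tests for categorical ones. If pairing of consecutive enrollees within an age range really was intended, the plan should say so and state how incomplete pairs are handled.

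The cost is one sentence. No participants, visits, measurements or sample-size changes are needed.

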# 14.0 Follow-up and Record Retention

Session numbers 8 and 9 will be follow-up and retention assessment sessions. Session 8 will occur 3-5 days after the last intervention day and session 9 will occur 4 weeks after the last day of intervention. The data will be retained for 3 years after the end of the study.

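### Section 11.0 states intention to treat, but the planned repeated measures ANOVA, as conventionally run, drops anyone who misses session 8 or 9, and the all-sessions rule excludes others before that

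*Combined protocol and SAP*

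**What the plan says.** Section 11.0 contains four statements that bear on this point.

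- Principle: "Intention to treat analysis will be used for addressing effects of treatment or control on static and dynamic balance".
- Analysis set: "Data from participants who engage in all the intervention sessions will be included in the analysis".
- Method: "Two-way repeated measures ANOVA (analysis of variance) will be used to determine" the group, time and group-by-time effects. On software: "SPSS (Statistical Package for the Social Sciences) and MATLAB will be used for processing and analyzing the data". No SPSS procedure is named and the time points are not listed.
- Expected loss: "To account for the likelihood of attrition and noncompliance, total 40 participants are being recruited". The stated requirement is 14 per group. No attrition rate is given.

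The visit schedule supplies the time points. Section 7.0 says "Study participation will require 9 visits: 1 pre-intervention visit, 6 intervention visits, 1 post-intervention visits and 1 retention visit", and its item 4 adds "Session 9 will be 4 weeks after session 7". Balance is therefore measured three times: at session 1, session 8 and session 9. Section 3.1 adds that a participant who cannot complete the gait assessment after two reschedulings leaves the study. No section describes imputation, a mixed model or any other handling of a missed assessment.

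**The concern.** A conventional repeated measures ANOVA (in SPSS, the general linear model procedure for repeated measures) needs a value at every time point and removes the whole case if one is absent. Someone who completes all six training sessions and is measured at session 8, but does not return four weeks later, would lose the baseline and session-8 values as well. The end-of-training comparison would then depend on who came back for a later visit. If return is related to the session-8 result, and differently by arm, that comparison is biased. If it is not, information is still wasted.

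There is a second conflict in the same section. Limiting the analysis to people who took part in all training sessions removes allocated participants because of what happened after allocation, so the stated principle fails even if nobody misses an assessment. The two problems need separate changes: removing the all-sessions rule leaves the listwise deletion, and changing the model leaves the all-sessions rule.

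**Working it through.** **1. Does the plan's sample size fit a three-assessment model?** Inputs from section 11.0: f = 0.25, alpha 0.05, power 0.8, 14 per group. Assumed, because not stated: correlation ρ = 0.5 and sphericity. For the group-by-time interaction with k = 2 groups and m = 3 measurements:

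λ = f² × N × m / (1 − ρ) = 0.0625 × 28 × 3 / 0.5 = 10.5, with (k − 1)(m − 1) = 2 and (N − k)(m − 1) = 52 degrees of freedom and critical F = 3.175. Power = 0.812.

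N = 26 gives 0.778, so 28 (14 per group) is reproduced. With two measurements the answer would be 34. The stated figure therefore fits an analysis that uses all three assessments. It depends on ρ: 38 at ρ = 0.3 and 18 at ρ = 0.7.

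**2. How much loss does recruiting 40 absorb?** 1 − 28/40 = 30%. Power of the interaction test by number of complete cases (ρ = 0.5):

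| Complete cases | 40 | 36 | 32 | 28 | 26 | 20 |
|---|---|---|---|---|---|---|
| Power | 0.935 | 0.906 | 0.866 | 0.812 | 0.778 | 0.648 |

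If sessions 8 and 9 were missed independently at the same rate p, complete cases would be 40(1 − p)². That reaches 28 at p = 1 − √0.7 = 16%.

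**3. Precision at session 8 when only session 9 is missed.** With ρ = 0.5 the SD of change is √(2(1 − 0.5)) = 1, so the SE of the difference in change is √(2/n per arm). The loss rates are assumptions.

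| Session-9 loss | Complete cases | SE, complete cases | SE, all session-8 data |
|---|---|---|---|
| 10% | 36 | √(2/18) = 0.333 | √(2/20) = 0.316 |
| 20% | 32 | √(2/16) = 0.354 | 0.316 |
| 30% | 28 | √(2/14) = 0.378 | 0.316 |

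**4. Bias at session 8.** This is a simulation with 10,000 trials per setting, 20 per arm, baseline to session-8 correlation 0.7, no true effect, and a baseline-adjusted session-8 contrast. Session-9 loss occurs at the same rate in both arms. In one arm it depends on the session-8 result given baseline, with a log-odds slope of 1.0 to 1.5 per SD. The ranges cover slopes scaled to the outcome SD and to the residual SD.

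| Session-9 loss | Bias, complete cases | False-positive rate, complete cases |
|---|---|---|
| 5% | 0.02 to 0.04 SD | about 5% to 6% |
| 10% | 0.05 to 0.09 SD | about 5% to 6% |
| 25% | 0.12 to 0.20 SD | 7% to 12% |

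Using all session-8 data gives no bias and about 5%. That follows from the set-up, because nobody misses session 8 here.

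**5. Loss completely at random.** With 25% loss and a true session-8 difference of 0.8 SD there is no bias. Power is 0.82 on complete cases against 0.92 to 0.93 with all session-8 data. If half of that loss happens before session 8, the comparison is about 0.82 against 0.87 to 0.88.

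**The case against.** Four objections carry weight.

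- **Listwise deletion is not a stated rule.** SPSS also has a mixed-model procedure and the plan names neither. This stands as a caveat. Even so, the method named is an ANOVA, and leaving the choice open allows it to be made after the data are seen.
- **Power is largely covered.** A reader might infer that the trial becomes underpowered. The figures do not support that: under ρ = 0.5 the planned interaction test stays at about 0.81 with 28 complete cases. Over-recruitment does not, however, remove bias.
- **The 12 extra participants are not a forecast of missed session-9 visits.** A reader might take 40 against 28 as an expected 30% loss at the last visit. Section 11.0 gives the margin for attrition and noncompliance together and states neither a rate nor a time. People who stop during training may leave no session-8 data to recover.
- **The bias scenario stacks assumptions.** It places all loss at session 9, makes it outcome-dependent in one arm, and evaluates a session-8 contrast that section 11.0 does not specify. Neither the planned ANOVA nor a mixed model was itself simulated. One might suppose that handing back the console at session 8 makes families in the gaming arm less likely to return. The documents give no evidence of this, and the gift card after each session applies to both arms.

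A further tempting reading is that the ANOVA alone turns intention to treat into a complete-case analysis. It does not: the all-sessions rule breaks the principle first.

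**Conclusion.** The point holds as a conditional gap. The plan expects attrition, states intention to treat, names a method that in its usual form keeps only participants with all three assessments, and says nothing about the rest. Separately, it contradicts intention to treat by its own analysis-set sentence.

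The main harm is possible bias and discarded session-8 data, with power a lesser matter. At 5% to 10% session-9 loss the effect is small even under unfavourable assumptions; it becomes material at about 25%. All these sizes rest on assumed loss rates, slopes and correlations. The three-assessment reading rests on the visit schedule and on the reproduction of 28. This should be fixed before analysis, but the documents do not support calling the planned analysis invalid.

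**What to change.** Make two changes in section 11.0.

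1. Replace the ANOVA with a linear mixed model for repeated measures (SPSS MIXED). Use group, time (sessions 1, 8 and 9) and group-by-time as fixed effects, an unstructured covariance, and Satterthwaite or Kenward-Roger degrees of freedom. Fit it by likelihood to every available assessment of every allocated participant, analysed in the allocated group.
2. Reconcile the all-sessions sentence with intention to treat by stating that participants who took part in all six training sessions form a supportive per-protocol analysis. The mixed model does not resolve this conflict unless that sentence is changed too.

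The cost is a few sentences and slightly more analysis work in software already named. Visits, sample size and participant burden do not change. The model still assumes that data are missing at random given the observed assessments. That is weaker than the completely-at-random assumption complete cases generally need, but it cannot be verified from the data. Participants who leave before session 8 contribute only their baseline.
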